8.3.5 Adverse Events Based on Signs and Symptoms

All AEs spontaneously reported by the participant or care provider or reported in response to the open question from the study site staff: ‘Have you/the child had any health problems since the previous visit/you were last asked?’ or revealed by observation will be collected and recorded in the eCRF. When collecting AEs, the recording of diagnoses is preferred (when possible) to recording a list of signs and symptoms. However, if a diagnosis is known and there are other signs or symptoms that are not generally part of the diagnosis, the diagnosis and each sign or symptom will be recorded separately.

Diagnoses of suspected or confirmed COVID-19, confirmed asymptomatic SARS-CoV-2 infection, and/or recurrence of COVID-19 (or of SARS-CoV-2 reinfection) will be collected and recorded in the eCRF as an AE. Additionally, if a participant has prolonged COVID-19 for approximately 3 months, then an AE of post-acute COVID (“long COVID”) will be recorded in the eCRF as an AE (In the case of post-COVID, symptoms may be of new onset following initial recovery from an acute COVID-19 episode, persist from the initial illness, or fluctuate/relapse over time; [WHO 2021](#)).

8.3.6 Adverse Events Based on Examinations and Tests

The results from the CSP-mandated laboratory tests/vital signs/ECG will be summarized in the CSR.

Deterioration as compared to baseline in protocol-mandated laboratory tests/vital signs/ECG should therefore only be reported as AEs if they fulfill any of the SAE criteria, are the reason for discontinuation of treatment with the IMP, or are considered to be clinically relevant as judged by the Investigator (which may include but is not limited to consideration as to whether treatment or non-planned visits were required or other action was taken with the IMP, eg, dose adjustment or drug interruption).

If deterioration in a laboratory value/vital sign/ECG is associated with clinical signs and symptoms, the sign or symptom will be reported as an AE and the associated laboratory result/vital sign will be considered as additional information. Wherever possible the reporting Investigator uses the clinical, rather than the laboratory term (eg, anemia versus low hemoglobin value). In the absence of clinical signs or symptoms, clinically relevant deteriorations in non-mandated parameters should be reported as AE(s).

Any new or aggravated clinically relevant abnormal medical finding at a physical examination as compared with the baseline assessment will be reported as an AE.

8.3.7 Hy's Law

Cases where a participant shows elevations in liver biochemistry may require further evaluation. Any occurrences of AST or ALT $\geq 3 \times$ ULN together with TBL $\geq 2 \times$ ULN and confirmed as a Hy's Law case should be reported as SAEs.

Aspartate aminotransferase or ALT $\geq 3 \times$ ULN together with TBL $\geq 2 \times$ ULN, where no other reason, other than the IMP, can be found to explain the combination of increases, eg, elevated ALP indicating cholestasis, viral hepatitis, another drug should be evaluated. The elevation in transaminases must precede or be coincident with (ie, on the same day) the elevation in TBL, but there is no specified timeframe within which the elevations in transaminases and TBL must occur.

Please refer to [Appendix D](#) for further instruction on cases of increases in liver biochemistry and evaluation of Hy's Law.

8.3.8 Reporting of Serious Adverse Events

All SAEs have to be reported, whether or not considered causally related to the IMP or to the study procedure(s). All SAEs will be recorded in the eCRF.

If any SAE occurs in the course of the study, investigators or other site personnel will inform the appropriate AstraZeneca representatives within one day ie, immediately but **no later than 24 hours** of when he or she becomes aware of it.

The designated AstraZeneca representative will work with the Investigator to ensure that all the necessary information is provided to the AstraZeneca Patient Safety data entry site **within one calendar day** of initial receipt for fatal and life-threatening events **and within 5 calendar days** of initial receipt for all other SAEs.

For fatal or life-threatening AEs where important or relevant information is missing, active follow-up will be undertaken immediately. Investigators or other site personnel will inform AstraZeneca representatives of any follow-up information on a previously reported SAE within one calendar day, ie, immediately but **no later than 24 hours** of when he or she becomes aware of it.

Once the investigators or other site personnel indicate an AE is serious in the EDC system, an automated email alert is sent to the designated AstraZeneca representative.

If the EDC system is not available, then the Investigator or other study site staff reports an SAE to the appropriate AstraZeneca representative by telephone.

The AstraZeneca representative will advise the Investigator/study site staff how to proceed.

For further guidance on the definition of a SAE, see [Appendix B](#).

The reference document for definition of expectedness/listedness is the IB for the AstraZeneca drug.

8.3.9 Pregnancy

All pregnancies and outcomes of pregnancy should be reported to AstraZeneca except for:

- If the pregnancy is discovered before the study participant has received any IMP.

8.3.9.1 Maternal Exposure

If a participant becomes pregnant during the course of the study, the decision to continue or discontinue the IMP will be left to the participant and the Investigator. The IMP should only be administered during pregnancy if the potential benefit outweighs the potential risk for the mother and the fetus.

Pregnancy itself is not regarded as an AE unless there is a suspicion that the IMP under study may have interfered with the effectiveness of a contraceptive medication. Congenital anomalies/birth defects and spontaneous miscarriages should be reported and handled as

SAEs. Elective abortions without complications should not be handled as AEs. The outcome of all pregnancies (spontaneous miscarriage, elective termination, ectopic pregnancy, normal birth, or congenital anomaly/birth defect) should be followed up and documented even if the participant was discontinued from the study.

If any pregnancy occurs in the course of the study, then the Investigator or other site personnel informs the appropriate AstraZeneca representatives within **1 day**, ie, immediately but **no later than 24 hours** of when he or she becomes aware of it.

The designated AstraZeneca representative works with the Investigator to ensure that all relevant information is provided to the AstraZeneca Patient Safety data entry site **within 1 or 5 calendar days** for SAEs (see Section 8.3.8) and **within 30 days** for all other pregnancies.

The same timelines apply when outcome information is available.

The PREGREP module in the eCRF is used to report the pregnancy, and the paper-based PREGOUT module is used to report the outcome of the pregnancy.

8.3.9.2 Paternal Exposure

In case of pregnancy of the partner of a male participant, the partner's pregnancy should be reported on the pregnancy form (consent from the partner must be obtained before the pregnancy form is completed) following the same timeframe and routing as described for any participant's pregnancy. Pregnancy of the participant's partner is not considered to be an AE. These pregnancies will also be followed up, and the outcome of the pregnancy (spontaneous miscarriage, elective termination, ectopic pregnancy, normal birth, or congenital abnormality) should, if possible, be obtained and documented.

8.3.10 Medication Error, Drug Abuse, and Misuse

8.3.10.1 Timelines

If an event of medication error, drug abuse, **or** drug misuse occurs during the study, then the Investigator or other site personnel informs the appropriate AstraZeneca representatives within **1 calendar day**, ie, immediately but **no later than 24 hours** of when he or she becomes aware of it.

The designated AstraZeneca representative works with the Investigator to ensure that all relevant information is completed within **1** (Initial Fatal/Life-Threatening or follow-up Fatal/Life-Threatening) **or 5** (other serious initial and follow-up) **calendar days** if there is an SAE associated with the event of medication error, drug abuse, or misuse (see Section 8.3.8) and **within 30 days** for all other events.

The definition of a Medication Error can be found in Appendix B 4.

8.3.10.2 Medication Error

For the purposes of this clinical study a medication error is defined as an **unintended** failure or mistake in the treatment process for an IMP or AstraZeneca NIMP that either causes harm to the participant or has the potential to cause harm to the participant.

The full definition and examples of medication error can be found in Appendix B 4.

8.3.10.3 Drug Abuse

Drug abuse is the persistent or sporadic **intentional**, non-therapeutic excessive use of IMP or AstraZeneca NIMP for a perceived reward or desired non-therapeutic effect.

The full definition and examples of drug abuse can be found in Appendix B 4.

8.3.10.4 Drug Misuse

Drug misuse is the **intentional** and inappropriate use (by a study participant) of IMP or AstraZeneca NIMP for medicinal purposes outside of the authorised product information, or for unauthorised IMPs or AstraZeneca NIMPs, outside the intended use as specified in the protocol and includes deliberate administration of the product by the wrong route.

The full definition and examples of drug misuse can be found in Appendix B 4.

8.4 Overdose

For this study, any dose of IMP (or dosing frequency) greater than what is specified in this protocol will be considered an overdose (see Table 6).

- An overdose with associated AEs is recorded as the AE diagnosis/symptoms on the relevant AE modules in the eCRF and on the Overdose eCRF module.
- An overdose without associated symptoms is only reported on the Overdose eCRF module.

If an overdose on an AstraZeneca study intervention occurs in the course of the study, the Investigator or other site personnel inform appropriate AstraZeneca representatives immediately, but **no later than 24 hours** of when he or she becomes aware of it.

The designated AstraZeneca representative works with the Investigator to ensure that all relevant information is provided to the AstraZeneca Patient Safety data entry site **within 1 or 5 calendar days** for overdoses associated with an SAE (see section 8.3.8) and **within 30 days** for all other overdoses.

8.5 Human Biological Samples

Instructions for the collection and handling of biological samples will be provided in the study specific laboratory manual. Samples should be stored in a secure storage space with adequate

measures to protect confidentiality. For further details on Handling of Human Biological Samples see [Appendix C](#).

Samples will be stored for a maximum of 15 years from the date of the issue of the CSR in line with consent and local requirements, after which they will be destroyed/repatriated.

- Pharmacokinetic samples will be disposed of after the Bioanalytical Report finalization or 6 months after issuance of the draft Bioanalytical Report (whichever is earlier), unless consented for future analyses.
 - Pharmacokinetic samples may be disposed of or anonymized by pooling. Additional analyses may be conducted on the anonymized, pooled pharmacokinetic samples to further evaluate and validate the analytical method. Any results from such analyses may be reported separately from the CSR.
- Remaining ADA sample aliquots will be retained at AstraZeneca or its designee for a maximum of 15 years following issue of the CSR. Additional use includes but is not limited to further characterization of any ADAs, confirmation and/or requalification of the assay as well as additional assay development work. The results from future analysis will not be reported in the CSR.

8.5.1 Pharmacokinetics

- Serum samples will be collected for measurement of serum concentrations of AZD7442 (tixagevimab and cilgavimab) as specified in the SoA (Section 1.3).
- Samples may be collected at additional time points during the study if warranted and agreed upon between the Investigator and the Sponsor, eg, for safety reasons. The timing of sampling may be altered during the course of the study based on newly available data (eg, to obtain data closer to the time of peak or trough matrix concentrations) to ensure appropriate monitoring.
- Serum samples will be used to analyse the PK of AZD7442. Samples collected for analyses of AZD7442 serum concentration may also be used to evaluate safety or efficacy aspects related to concerns arising during or after the study.
- Samples will be collected, labeled, stored, and shipped as detailed in the Laboratory Manual.

8.5.1.1 Determination of Drug Concentration

Samples for determination of drug concentration in serum will be assayed by bioanalytical test sites operated by or on behalf of AstraZeneca, using an appropriately validated bioanalytical method. Full details of the analytical method used will be described in a separate bioanalytical report.

Incurred sample reproducibility analysis, if any, will may be performed alongside the bioanalysis of the test samples. The results from the evaluation, if performed, will be reported in a separate Bioanalytical Report.

8.5.2 Immunogenicity Assessments

Serum samples for immunogenicity assessments will be collected according to the SoA (Section 1.3).

Samples will be collected, labeled, stored, and shipped as detailed in the Laboratory Manual.

8.5.2.1 Antidrug Antibody Assessments

Blood samples for determination of ADA in serum will be assayed by bioanalytical test sites operated by or on behalf of AstraZeneca, using an appropriately validated bioanalytical method. Full details of the methods and analyses performed will be described in a separate bioanalytical report.

Unscheduled samples for ADA analysis should be collected in response to suspected immune-related AEs.

The presence or absence of ADA will be determined in the serum samples using a validated bioanalytical method. A tiered testing scheme will be employed, with the first step being screening. Samples found positive in the screening step will be tested in the confirmatory step. Samples confirmed positive for ADA in the confirmatory step will undergo endpoint titer determination.

8.5.2.2 SARS-CoV-2 Serology Assessments

Serum samples will be collected to assess SARS-CoV-2 antigen-specific antibody levels. Baseline serostatus and the rate of SARS-CoV-2 infection in participants receiving AZD7442 will be determined by seroconversion (negative to positive) in a validated SARS-CoV-2 N protein antigen assay operated by an authorized laboratory.

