4 STUDY DESIGN

4.1 Overall Design

This is a Phase II randomized, open-label, multicenter, dose-ranging study to assess the safety, immunogenicity, PK, and PD profiles of AZD7442 repeat dose regimens. The study will enroll adults and pediatric individuals (≥ 12 years of age weighing at least 40 kg) who are moderate to severely immunocompromised due to an underlying disease or are taking immunosuppressive medications and therefore unable to mount an adequate immune response to COVID-19 vaccine.

Approximately 200 adults and pediatric individuals, who meet the eligibility criteria, will be randomized in a 1:1 ratio to one of 2 AZD7442 treatment arms:

- Arm A (100 participants): AZD7442 600 mg administered intramuscularly (IM) on Day 1 followed by 300 mg IM Q3M for 12 months (a total of 5 doses)
- Arm B (100 participants): AZD7442 1200 mg administered intravenously (IV) on Day 1 followed by 600 mg IM Q6M for 12 months (a total of 3 doses)

An EoT Visit will be conducted at 15 months in both arms (3 months after the final dose of AZD7442).

After the EoT Visit, the participant will enter the follow-up period. Participants will be followed for safety for an additional 9 months after the EoT Visit, ie, through 12 months after the participant's final dose of AZD442.

Participants who permanently discontinue IMP administration due to the premature termination of the study will remain in the study to complete visits/assessments (except those

related to monitoring of IMP administration) for at least 6 months after their final dose of AZD7442.

The total duration of the study for a participant is 105 weeks (approximately 24 months) for both arms which includes the screening period (up to one week), the treatment period (15 months), and the follow-up period (9 months).

An independent DSMB will provide oversight, to ensure safe and ethical conduct of the study (see Section 9.6 and Appendix A 5.1).

The study design is presented [Figure 1](#).

4.1.1 Study Conduct Mitigation During Study Disruptions Due to Cases of Civil Crisis, Natural Disaster, or Public Health Crisis

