5.1 Inclusion Criteria

Participants are eligible to be included in the study only if all of the following criteria apply:

Informed Consent

- 1 Capable of giving signed informed consent as described in [Appendix A](#) which includes compliance with the requirements and restrictions listed in the ICF and in this protocol. For pediatric participants: informed assent is to be provided by the participant; informed consent must be provided by the participant's legal guardian (see [Appendix A 3](#)).
- 2 Ensure that participants who are considered by the Investigator clinically unable to consent at screening and who are entered into the study by the consent of a legally acceptable representative show evidence of assent, as applicable in accordance with local regulations. See [Appendix A](#) for further details.

Age

- 3 Participant must be an adult (≥ 18 years of age) or pediatric individual (≥ 12 to < 18 years of age weighing ≥ 40 kg) at the time of signing the ICF or assent (for pediatric participants).

Type of Participant and Disease Characteristics

- 4 Individuals with medical conditions or treatments that may result in moderate to severe immune compromise or an inadequate immune response to COVID-19 vaccination include but are not limited to:
 - (a) Active treatment for solid tumor and hematologic malignancies.
 - (b) Receipt of solid-organ transplant and taking immunosuppressive therapy.
 - (c) Receipt of chimeric antigen receptor T-cell or hematopoietic stem cell transplant (within 2 years of transplantation or taking immunosuppression therapy).

- (d) Moderate or severe primary immunodeficiency (eg, DiGeorge syndrome, Wiskott-Aldrich syndrome).
 - (e) Advanced or untreated HIV infection (people with HIV and history of CD4 cell counts $< 200/\text{mm}^3$, history of an AIDS-defining illness without immune reconstitution, or clinical manifestations of symptomatic HIV).
 - (f) Active treatment with systemic high-dose corticosteroids (ie, ≥ 20 mg prednisone or equivalent per day when administered for ≥ 2 weeks), alkylating agents, antimetabolites, transplant-related immunosuppressive drugs, cancer chemotherapeutic agents classified as severely immunosuppressive, tumor necrosis factor blockers, and other biologic agents that are immunosuppressive or immunomodulatory (eg, B-cell depleting agents).

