6.5 Concomitant Therapy

Any medication or vaccine (including COVID-19 vaccines, over-the-counter or prescription medicines, vitamins, and/or herbal supplements) that the participant is receiving at the time of enrollment or receives during the study must be recorded along with:

- Reason for use
- Dates of administration including start and end dates
- Dosage information including dose and frequency

The Study Physician should be contacted if there are any questions regarding concomitant or prior therapy.

Table 7 lists the permitted, restricted, and prohibited medications during the study.

Table 7 Permitted, Restricted, and Prohibited Medications

Use Category	Type of medication/treatment	Timeline/instructions
Permitted	Routine Vaccines	Licensed influenza vaccines are permitted at any time. All other routine vaccines are permitted; however, they should not be given within 14 days before or after any dose of IMP. Vaccines for the prevention of SARS-CoV-2 or COVID-19 are not considered routine vaccines in this protocol and are allowed; however, they should not be given within 14 days before or after any dose of IMP (see Section 6.5.1).
	Allergen immunotherapy	Allowed if participant has been receiving stable desensitization therapy for allergies for at least 30 days prior to screening and there is no anticipated change during the treatment period. Allergen immunotherapy should not be administered on the same day as IMP. Non-prescription over-the-counter treatments for allergies such as antihistamines, decongestants, and nasal steroids are permitted for such participants.

Table 7 Permitted, Restricted, and Prohibited Medications

Use Category	Type of medication/treatment	Timeline/instructions
	Commercial biologics, prednisone, immunosuppressive medications (eg, azathioprine, tacrolimus, cyclosporine, methotrexate, or cytotoxic chemotherapy)	Allowed. Biologics (eg, palivizumab, adalimumab) should not be administered on the same day as IMP.
	IVIG	Allowed for participants with primary or secondary immunodeficiency who have hypoglobulinemia and need replacement IVIG. IVIG should not be administered on the same day as IMP.

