4.2.3.4 Analysis of Exploratory Endpoints

4.2.3.4.1 SARS-CoV-2 RT-PCR-positive Symptomatic Illness

The incidence of SARS-CoV-2 RT-PCR-positive symptomatic illness will be summarized with descriptive statistics in the FAS at the final data readout only. The number and percentage of participants who have the events will be provided overall and before Day 183, or Day 365.

Participants will be included as an event if they have RT-PCR-confirmed SARS-CoV-2 prior to Day 183, or Day 365, after first IMP dose and present with at least one of the qualifying symptoms as defined in the CSP. A positive SARS-CoV-2 RT-PCR will be defined based on the central laboratory result whenever both central and local laboratory results are available for NP swabs, or if only a central lab NP swab result is available. If only a local NP swab laboratory result is available, then the local laboratory result will be used. If no SARS-CoV-2 RT-PCR results are available, the participant will be considered as not having a RT-PCR-positive symptomatic event. Data from the eCRF will be used to determine if the participant met the qualifying symptoms. If a participant's first case of SARS-CoV-2 RT-PCR positive symptomatic illness occurs on or after Day 183, or Day 365, the participant will be considered as not having an event, respectively. Death due to COVID-19 or hospitalization due to COVID-19 can contribute to this endpoint when a qualifying symptom assessment is not observed.

- For participants with an event after first IMP dose, before Day 183, or Day 365, the date of event will be defined as the earliest symptom onset date from those which triggered an illness visit, where COVID-19 was confirmed with a positive SARS-CoV-2 RT-PCR laboratory test. In the case of death due to COVID-19 or hospitalization due to COVID-19, the date of event is the earliest date of death/date of hospital admission when a qualifying symptom is not observed.

If any of the following censoring reasons are met, the censoring date will be defined as follows:

- Participants who had SARS-CoV-2 RT-PCR positive test prior to first IMP dose will be censored at date of first IMP dose.
- Participants who receive a COVID-19 vaccination after first IMP dose, and prior to having an event before Day 183, or Day 365 will be censored at the date of vaccination.

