4.2.3.4.2 Post-treatment Response for SARS-CoV-2 Nucleocapsid Antibodies

The incidence of participants who have a post-treatment response (negative at baseline to positive at any time post-baseline) for SARS-CoV-2 nucleocapsid antibodies will be summarized using FAS by treatment group overall and before Day 183, or Day 365 at the final data readout only. Same censoring criteria as described in Section 4.2.3.4.1 will be applied.

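### Nucleocapsid seroconversion alone will understate infection in participants expected to form antibody poorly, and no planned table sets it against RT-PCR

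*Protocol*

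**What the plan says.** Protocol 8.5.2.2 states that "the rate of SARS-CoV-2 infection in participants receiving AZD7442 will be determined by seroconversion (negative to positive" in a validated N-protein assay. It names no other test for this purpose.

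Protocol 4.1 describes the participants as immunocompromised and "therefore unable to mount an adequate immune response to COVID-19 vaccine". Inclusion criterion 4 in Protocol 5.1 covers primary immunodeficiency, transplant immunosuppression and "other biologic agents that are immunosuppressive or immunomodulatory (eg, B-cell depleting agents", among others.

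The endpoint itself is defined in SAP 4.2.3.4.2 as a "post-treatment response (negative at baseline to positive at any time post-baseline) for SARS-CoV-2 nucleocapsid antibodies". It is summarised in the full analysis set, overall and before Day 183 or Day 365. On follow-up the SAP says: "Same censoring criteria as described in Section 4.2.3.4.1 will be applied". The borrowed rules in SAP 4.2.3.4.1 cover a positive RT-PCR before the first dose, COVID-19 vaccination, restricted-medication deviations, certain PK-related deviations and early discontinuation.

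RT-PCR-positive symptomatic illness is a separate exploratory endpoint under the same objective (Protocol Table 5, SAP 4.2.3.4.1). Protocol 8.1.1 starts Illness Visits, and with them local and central RT-PCR, when a participant has suspected COVID-19 symptoms. The schedules in Protocol 1.3 contain no other RT-PCR after Day 1. SAP 4.2.3.5 plans no sensitivity analysis for the exploratory endpoints.

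**The concern.** A seroconversion count measures infection multiplied by the chance that an infected person makes detectable anti-N antibody. In a trial that selects for impaired antibody formation, the second factor cannot be taken as close to one. Every infected participant who does not respond becomes a non-event in a figure that Protocol 8.5.2.2 calls the rate of infection.

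The absolute level matters because both arms receive AZD7442. There is no untreated group against which a shared under-count would partly cancel, so a reader looking for the frequency of infection under AZD7442 will take the percentage at face value. The RT-PCR endpoint does not fill the gap for asymptomatic infection, because testing follows symptoms. Scheduled serology is the study's only systematic check there, and that is where a poor antibody response does most harm.

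**Working it through.** **1. Plan's own figures.** The documents give no infection risk, no assay sensitivity in this population and no baseline seropositive share. The plan's one computed figure is the sample-size statement: 1 - 0.97^100 = 0.952, which agrees with the stated 95%. It concerns adverse events and has no bearing here.

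**2. How one participant is classified.** Take a participant who is N-negative at baseline, falls ill, has a positive RT-PCR and never becomes N-positive.

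- SAP 4.2.3.4.1: an event, provided a qualifying symptom, COVID-19 hospitalisation or COVID-19 death is recorded and no censoring rule applies first.
- SAP 4.2.3.4.2: not an event, because only a change from negative to positive counts.
- Any table showing both results together: none is planned.

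If the same participant has no symptoms, the study takes no RT-PCR. The infection then appears in neither endpoint. It would be recorded only as an adverse event, and only if it were confirmed outside the study's own testing (Protocol 8.1.1 and 8.3.5).

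**3. Size under assumed inputs.** Let t be the true infection risk among baseline-negative participants and s the proportion of infected participants who seroconvert. With no false positives, the reported rate is t x s and the missed infections are t x (1 - s).

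| t (assumed) | s = 0.5 | s = 0.7 | s = 0.9 |
|---|---|---|---|
| 10% | 5% | 7% | 9% |
| 20% | 10% | 14% | 18% |
| 30% | 15% | 21% | 27% |

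At t = 20%, 10, 6 or 2 infections per 100 are missed. The reported rate divided by the true rate is simply s.

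**4. Denominator.** SAP 3.3 uses the whole analysis set as the denominator unless stated otherwise, and SAP 4.2.3.4.2 states nothing else. Prior COVID-19 infection is not an exclusion (Protocol 5.2), so some participants may be N-positive at baseline and unable to seroconvert. If their share is b, the reported percentage becomes (1 - b) x t x s, a second downward factor.

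**5. Passive antibody, as a hypothetical only.** Let f be the share using IVIG and q the chance that IVIG turns a negative sample positive. The reported rate is t x s + t x (1 - s) x f x q + (1 - t) x f x q. Take t = 0.20 and s = 0.7.

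- With f = 0.10 and q = 0.25: 0.14 + 0.0015 + 0.02 = 16.2%.
- With f = 0.20 and q = 0.5: 0.14 + 0.006 + 0.08 = 22.6%.

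The second case exceeds the true 20%, so passive conversion on that scale would reverse the direction of the error. The documents support no value of f or q.

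**The case against.** The best reply is that the plan already separates the two measures. RT-PCR-positive illness has its own definition, incidence and Kaplan-Meier analysis. Severe cases and COVID-19 deaths are summarised too. Protocol Table 5 and the SAP name the serology endpoint a nucleocapsid antibody response, so the mislabelling is confined to one sentence in a section on sample assessments. The endpoint is exploratory and descriptive, and no hypothesis is tested. All of this stands, and it keeps the point minor. It does not supply the missing cross-tabulation or correct the sentence in 8.5.2.2.

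A reader might infer three stronger conclusions that the documents do not support.

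- *RT-PCR-confirmed cases are treated as uninfected by the trial.* They are absent only from the serology figure. Symptomatic cases are counted in the neighbouring endpoint.
- *Participants are selected for proven non-response.* Inclusion criterion 4 lists conditions and treatments that may impair response. It requires no documented failure, and it speaks of vaccination, not of anti-N response to infection. A reduced response is expected, not shown.
- *IVIG will be counted as infection.* Protocol Table 7 says of IVIG "Allowed for participants with primary or secondary immunodeficiency who have hypoglobulinemia and need replacement IVIG", and no SAP censoring rule names it. But the documents do not say that any participant receives it or that the product contains anti-N antibody. Someone already on such a product might be positive at baseline and could not seroconvert. Convalescent plasma is in the restricted category, so its use is already censored when recorded as a deviation.

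**Conclusion.** The concern holds in limited form. Read as the infection rate, the serology figure is too low by the factor s, and by a further factor if baseline-seropositive participants stay in the denominator. The 10-18% against a true 20% is an illustration: neither the 20% risk nor the 50-90% seroconversion range comes from the documents, and the actual shortfall cannot be computed from them. The downward direction rests on two premises: that some infected participants fail to seroconvert, which follows from the protocol's description of the population, and that passive or false-positive conversions do not offset the loss, which the documents neither show nor exclude.

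The primary endpoints, the secondary endpoints and the sample size are unaffected. Severity is minor.

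**What to change.** 1. In Protocol 8.5.2.2, call the measure N seroconversion, in line with Table 5 and SAP 4.2.3.4.2. If one sentence does not merit an amendment, SAP Section 2 can carry the clarification.
2. In SAP 4.2.3.4.2, state that the seroconversion percentage uses baseline-seronegative participants as its denominator.
3. Add a descriptive composite, RT-PCR positive (as defined in SAP 4.2.3.4.1) or seroconversion, at the time points already planned, with its denominator stated. Participants seropositive at baseline can enter it only through RT-PCR.
4. Show the number and percentage who seroconverted among baseline-seronegative RT-PCR-positive participants with a later serology sample. This is the trial's own evidence on s. It comes from symptomatic cases, so it need not apply to asymptomatic ones.
5. State that the composite still misses asymptomatic infections without seroconversion.
6. For IVIG, at most flag in a listing any conversion first seen after immunoglobulin newly started post-baseline. Do not remove it from the count: excluding all conversions after IVIG would also discard true infections in people on continuing replacement.

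The cost is one extra exploratory table, a short listing flag and a merge of serology with RT-PCR and concomitant-medication data that are already collected. No new samples are needed.
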